2. STUDY OBJECTIVES

2.1. Primary Objective

The primary objective of the study is to demonstrate that dupilumab treatment improves exercise capacity in patients with moderate-to-severe asthma.

2.2. Secondary Objectives

The secondary objectives of the study are:

- To demonstrate that dupilumab treatment increases physical activity of daily living in patients with moderate-to-severe asthma
- To demonstrate that dupilumab treatment improves pre- and post-exercise lung function in patients with moderate-to-severe asthma

2.3. Exploratory Objectives

The exploratory objectives of the study are:

- To demonstrate that dupilumab treatment decreases dynamic hyperinflation during constant work rate exercise in patients with moderate-to-severe asthma
- To demonstrate that dupilumab treatment improves perception of dyspnea
- To demonstrate that dupilumab treatment improves perception of leg fatigue
- To demonstrate that dupilumab treatment increases oxygen consumption during the constant work rate exercise test (CWRET)

- To demonstrate that dupilumab treatment improves asthma control in patients with moderate-to-severe asthma
- To demonstrate that dupilumab treatment improves asthma-related quality of life in patients with moderate-to-severe asthma
- To demonstrate that dupilumab treatment improves patients' impression of ability to carry out exercise
- To demonstrate that dupilumab treatment improves patients' impression of the impact that asthma has on the ability to perform exercise
- To demonstrate that dupilumab treatment decreases pre- and post-exercise FeNO
- To measure nocturnal awakenings due to asthma measured by patient diary

3. HYPOTHESIS AND RATIONALE

3.1. Hypothesis

Patients with moderate-to-severe asthma treated with dupilumab show improvement in exercise capacity and increase in physical activity of daily living.

3.2. Rationale

3.2.1. Rationale for Study Design

It has been shown that dupilumab treatment significantly improves FEV₁, asthma control and reduces type 2 mediated inflammation in patients with moderate-to-severe asthma (Castro, 2018) (Rabe, 2018) (Wenzel, 2016). This study will determine whether these improvements translate into (1) an increase in exercise capacity as measured by cycle ergometry and constant work rate exercise endurance time, and (2) an increase in physical activities of daily living assessed by accelerometry.

Effects of pharmacotherapy on exercise capacity and physical activity in patients with asthma have not been rigorously examined in clinical studies. Small studies in asthma with bronchodilators or bronchodilator + ICS intervention have shown inconsistent results regarding improvement in exercise capacity (Haverkamp, 2007) (Robertson, 1994). A 6-week study of patients with mild-to-moderate asthma treated with high dose fluticasone showed improvement in exercise endurance time and FEV₁ (Haverkamp, 2007). However, other studies in patients with asthma treated with bronchodilators demonstrated increases in FEV₁ without consistent improvement in exercise capacity (Freeman, 1989). An unblinded, small study of omalizumab in 20 consecutive patients with severe allergic asthma (10 receiving omalizumab and 10 placebo) demonstrated significant improvement in both FEV₁ and exercise capacity after 16 weeks of omalizumab treatment (Schaper, 2011).

Small, non-interventional, cross-sectional studies using various accelerometers worn at the wrist or hip have shown that patients with severe asthma walk approximately 27% to 30% fewer steps per day compared to age and gender matched healthy volunteers (mean steps/day severe asthma =

5362; range 3999 to 7817 vs. healthy controls 7817; range 6072 to 10014) (Cordova-Rivera, 2018). Studies evaluating FEV₁ as a marker of physical activity have shown conflicting results. Bahmer et al reported that FEV₁ and peak expiratory flow were poor markers of physical activity in asthma patients showing no significant correlation between FEV₁ and steps walked per day (Bahmer, 2017), whereas Hennegrave, et al showed significant correlation between steps walked and FEV₁ (Hennegrave, 2018).

Dupilumab has been shown to increase lung function and improve asthma control. It is hypothesized that this demonstrated efficacy may result in improvements in exercise capacity and physical activity of daily living. Pulmonary limitation to exercise will be identified by demonstrating a decrease in IC from pre-exercise to the value during the maximal incremental exercise test performed at screening.

This phase 4, randomized, placebo-controlled study is designed to evaluate whether treatment with dupilumab increases exercise endurance time evaluated using constant work rate exercise testing (CWRET). Additionally, physical activities of daily living (steps walked per day, energy expenditure, and time spent in moderate-to-vigorous activity) will be assessed using accelerometry.

A blinded, randomized design is chosen to minimize bias in data collection and result interpretation. The presence of a placebo arm is appropriate for the objectives of this study since it will provide the most robust assessment of the efficacy of dupilumab. A run-in period is planned to stabilize background asthma treatment, familiarize patients with the CWRET, determine an individualized work rate that a patient can tolerate for 3 to 8 minutes (180 to 480 seconds), and to collect pre-treatment accelerometry data. A 12-week treatment period is selected based on the findings in dupilumab clinical studies in moderate-to-severe asthma patients where near-maximal improvements in lung function occurred by approximately 8 to 12 weeks after treatment initiation. A 2-week post-treatment follow-up period is chosen to ensure clinical stability of patients after the treatment period is complete.

Cardiopulmonary exercise testing (CPET) has been utilized in several interventional studies to assess the degree of dynamic hyperinflation in patients with obstructive lung diseases, and its impact on exercise capacity (Benfante, 2018) (Casaburi, 2014) (Maltais, 2011) (O'Donnell, 2004). CPET can be performed on a stationary bicycle or a treadmill. Cycle ergometry has been selected over a treadmill protocol because it requires relatively little patient practice (unlike treadmill exercise) and the external power output is accurately known. A constant work-rate protocol is chosen to assess the primary endpoint versus a maximal incremental exercise test, as the former is more sensitive to discriminate change in exercise capacity. To minimize variability in the measurements, the CPET will be done using a standardized CPET protocol, and only at sites proficient in CPET and pulmonary function testing.

3.2.2. Rationale for Dose Selection

The dose regimen selected for this study is dupilumab 300 mg administered subcutaneously (SC) every other week (Q2W) with a 600 mg loading dose for the first dose. This dosing regimen is chosen as it has been shown to be efficacious, with an acceptable safety profile in asthma pivotal studies and is approved for the treatment of moderate-to-severe asthma, the patient population under study.

3.3. Risk-Benefit

Recognizing that the “Coronavirus Disease 2019” (COVID-19) pandemic will have an impact on the conduct of clinical trials, the sponsor does not intend to screen any new patients in this study unless the impact of the COVID-19 pandemic is deemed manageable and no longer interfering with the conduct of trials at individual sites, and patients can safely participate in this study. Until then, the sponsor plans to obtain approvals from Health Authorities/Ethics Committees to enable continuation of study sites for this study, as allowed by local laws and regulations.

Dupilumab has shown a favorable risk-benefit profile in patients with atopic dermatitis, asthma, and CRSwNP (see details in the DUPIXENT label and Dupilumab Investigator’s Brochure).

The study population consists of a moderate-to-severe asthma patient population studied in the phase 3 studies of the dupilumab asthma clinical program, and for which dupilumab has been shown to have a positive risk-benefit profile. The safety data available to date across multiple indications and risk-reducing measures planned in this study, in conjunction with the clinical benefit of dupilumab demonstrated in asthma patients, support a favorable risk-benefit profile for dupilumab for this study population.

Multiple studies have shown that patients with obstructive lung disease and decreased lung function can perform a CPET safely. A number of procedures are required to assure patient safety when performing a CPET. At screening, patients will be carefully evaluated to determine appropriateness for a CPET; those not appropriate for the test will be excluded from the study. Both relative and absolute contraindications including, but not limited to, uncontrolled arrhythmia, uncontrolled elevated blood pressure (systolic blood pressure >180 mm Hg or diastolic blood pressure >95 mm Hg), clinically significant coronary artery disease, unstable angina, etc, preclude participation in this study (a detailed list of absolute and relative contraindications for performing CPET is provided in Section 9.2.2.4, Table 2). Any patient who the investigator judges to be unsuitable for exercise regardless of CPET contraindications cannot enroll or continue in the study. A CPET will be performed only at pulmonary function test (PFT) labs experienced in performing CPET and according to the American Thoracic Society (ATS)/ European Respiratory Society (ERS) recommendations. Professionals experienced in performing CPET in patients with abnormal lung function, certified in advanced cardiac life support and experienced in interpreting physiologic responses to exercise will closely monitor each patient during the CPET. A number of physiologic responses are assessed repeatedly during CPET, including electrocardiogram (ECG) parameters, oxygen saturation, blood pressure, pulmonary ventilation, oxygen uptake, and respiratory rate. A medical doctor must be present in the room in which the initial incremental work rate exercise test (IWRET) is conducted and readily available for medical intervention, if needed, at all subsequent exercise tests. Resuscitation equipment must be immediately available in the PFT lab where the exercise testing is performed. A CPET laboratory manual, providing detailed instructions, including relative and absolute contraindications to testing and indications for exercise termination, will be distributed to each study site.

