7.3. Premature Withdrawal from the Study

A patient has the right to withdraw from the study at any time, for any reason, and without repercussion.

The investigator and/or sponsor have the right to withdraw a patient from the study if it is no longer in the interest of the patient to continue in the study, or if the patient's continuation in the study places the scientific outcome of the study at risk (eg, if a patient does not or cannot follow study procedures). An excessive rate of withdrawals would render the study uninterpretable; therefore, unnecessary withdrawal of patients should be avoided.

Patient who are withdrawn prematurely from the study will be asked to complete the early termination visit, as described in Section [9.1.2](#).

Rules for discontinuation of study treatment (permanent or temporary) are discussed in Section [8.5.2](#).

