8. STUDY TREATMENTS

8.1. Investigational and Reference Treatments

The study drug dosing regimen is dupilumab 600 mg loading dose on study day 1 and 300 mg Q2W from week 2 to week 10 or matching placebo.

Dupilumab drug product is supplied for this study in the following concentration:

- Dupilumab 150 mg/mL: Each 2.0 mL single-use prefilled glass syringe with snap-off cap delivers 300 mg of study drug (2.0 mL of a 150 mg/mL solution)

Placebo matching dupilumab is prepared in the same formulation without the addition of protein (ie, active substance, anti-IL-4R α mAb).

Study drug will be administered by SC injections. Subcutaneous injection sites of study drug should be alternated among the different quadrants of the abdomen (avoiding navel and waist areas), upper thighs, and upper arms so that the same site is not injected for 2 consecutive administrations. To allow for adequate assessment of possible injection site reactions (ISRs), study drug should be administered only into areas of normal looking skin. Instructions for recording and reporting ISRs will be provided in the study binder.

Patients and/or caregivers who are willing and able to self-administer some dupilumab doses outside of the clinic will be trained on injecting the study drug.

The procedure for preparing and administering dupilumab will be provided in the pharmacy manual.

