8.5.2. Study Drug Discontinuation

Patients who permanently discontinue from study drug should be encouraged to remain in the study. Those who agree and do not withdraw from the study will be asked to return to the clinic for all remaining study visits per the visit schedule.

Patients who permanently discontinue from study drug and who opt to withdraw from the study will be asked to complete study assessments, per Section [9.1.2](#).

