8.5.2.1. Reasons for Permanent Discontinuation of Study Drug

Study drug dosing will be permanently stopped in the event of:

- Evidence of pregnancy
- Serious or severe allergic reactions considered related to study drug
- Specific types of liver dysfunction (eg, Hy's law is met ([Guidance for Industry Drug Induced Liver Injury: Premarketing Clinical Evaluation FDA, 2009](#)))
- Patient withdraws consent
- If, in the investigator's opinion, continuation in the study would be detrimental to the patient's well-being
- In the event of a protocol deviation, at the discretion of the investigator or the Sponsor
- Any patient unblinding requested by the investigator will lead to permanent treatment discontinuation
- Diagnosis of a malignancy during study, excluding carcinoma in situ of the cervix, or squamous or basal cell carcinoma of the skin
- Other intercurrent illnesses or major surgery which could, in the opinion of the investigator, present an unreasonable risk to the patient as a result of his/her continued participation in the study
- Development of a condition that precludes exercise
- Infections or infestations that do not respond to medical treatment
- Any opportunistic infection, or other infections whose nature or course may suggest an immunocompromised status
- Serum ALT and/or AST $>3\times\text{ULN}$ with total bilirubin $>2\times\text{ULN}$, excluding confirmed Gilbert's syndrome
- Confirmed AST and/or ALT $>5\times\text{ULN}$ (for more than 2 weeks)
- Neutrophils $<1500/\text{mm}^3$
- Platelets $<100000/\text{mm}^3$
- Suspicion of rhabdomyolysis or CPK $>10\times\text{ULN}$

Any abnormal laboratory value or ECG parameter will be immediately rechecked for confirmation before making a decision of permanent discontinuation of the study drug for the concerned patient.

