9.1.2. Early Termination Visit

Patients who are withdrawn from the study before the primary endpoint visit (week 12) will be asked to return to the clinic once for an early termination visit consisting of the end of study assessments described in [Table 1](#).

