10. SAFETY EVALUATION AND REPORTING

10.1. Recording and Reporting Adverse Events

10.1.1. General Guidelines

The investigator must promptly record all clinical events occurring during the study data collection period, from the time of signing the informed consent form (ICF) to the end of study. Medical conditions that existed or were diagnosed prior to the signing of the Informed Consent will be recorded as part of medical history. Abnormal laboratory values and vital signs observed at the time of Informed Consent should also be recorded as medical history. Any subsequent worsening (ie, any clinically significant change in frequency and/or intensity) of a pre-existing condition that is temporally associated with the use of the study drug should also be recorded as an AE.

At each visit, the investigator will determine whether any AEs have occurred by evaluating the patient. Adverse events may be directly observed, reported spontaneously by the patient, or by questioning the patient at each study visit. Patients should be questioned in a general way, without asking about the occurrence of any specific symptoms. The Investigator must assess all AEs to determine seriousness, severity, and causality, in accordance with the definitions in Section 10.2. The investigator's assessment must be clearly documented in the site's source documentation with the investigator's signature. The investigator should follow up on serious adverse events (SAEs) and adverse events of special interest [AESIs]) until they have resolved or are considered clinically stable; AEs should be followed until they are resolved or last study visit, whichever comes first.

Always report the diagnosis as the AE or SAE term. When a diagnosis is unavailable, report the primary sign or symptom as the AE or SAE term with additional details included in the narrative until the diagnosis becomes available. If the signs and symptoms are distinct and do not suggest a common diagnosis, report them as individual entries of AE or SAE.

Laboratory results, vital signs, and other diagnostic results or findings should be appraised by the investigator to determine their clinical significance. Isolated abnormal laboratory results, vital sign findings, or other diagnostic findings (ie, not part of a reported diagnosis) should be reported as AEs if they are symptomatic, lead to study drug discontinuation, dose reduction, require corrective treatment, or constitute an AE in the investigator's clinical judgment.

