Primary (Continuous)	Change from baseline to week 12 in constant work rate exercise endurance time	FAS	
The intercurrent events will be handled as follows:
 
 Initiation of systemic corticosteroids for the treatment of an asthma exacerbation or increase in systemic corticosteroid dose for those receiving maintenance OCS, within the last 4 weeks of the double-blind treatment period: Constant work rate exercise endurance time for each patient at week 12 will be assigned by his/her baseline values of constant work rate exercise endurance time (Hypothetical strategy) Asthma exacerbation prior to week 8 of the double-blind treatment period requiring systemic corticosteroids or an increase in systemic corticosteroid dose for those receiving maintenance OCS: Data collected after the intercurrent event will be included in the analyses (Treatment policy strategy). Initiation of prohibited medications: Data collected after the intercurrent event will be included in the analyses (Treatment policy strategy). Treatment discontinuation: Data collected after the intercurrent event will be included in the analyses (Treatment policy strategy). 
Missing data imputation rules:
 
 BOCF will be used to impute the missing values for discontinuation of the study either due to AE or lack of efficacy. Missing data due to any other reason including COVID-19 will be imputed using multiple imputation (MI) 	Mean change from baseline/The ANCOVA model with treatment group, randomization stratification factors and the baseline value for the constant work rate exercise endurance time as covariates.

Subgroup analysis may be performed for age, sex, weight, baseline FEV₁, baseline constant work rate endurance time and baseline ACQ-5. Subgroup analyses may not be performed if the primary efficacy result is not statistically significant.

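### Read literally, Protocol 3.3 removes a randomized patient who becomes unfit for exercise, while 8.5.2 asks that patient to stay; no text says which rule applies

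*Protocol*

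**What the plan says.** - **Protocol 3.3 (Risk-Benefit):** "Any patient who the investigator judges to be unsuitable for exercise regardless of CPET contraindications cannot enroll or continue in the study".
- **Protocol 8.5.2.1** lists, among the reasons to stop study drug permanently, "Development of a condition that precludes exercise". The action named there is stopping the drug; leaving the study is not mentioned.
- **Protocol 8.5.2:** "Patients who permanently discontinue from study drug should be encouraged to remain in the study". Those who agree are asked back for every remaining visit. No reason for stopping is excepted.
- **Protocol 7.3** gives the investigator and sponsor a right to withdraw a patient, for instance one who does not or cannot follow study procedures. It also warns that too many withdrawals would make the study uninterpretable: "therefore, unnecessary withdrawal of patients should be avoided".
- **Protocol 9.1.1, footnote 4** requires a local ECG free of clinically significant abnormality before every exercise test, and makes this a condition of continuing in the study.
- **Protocol 8.4 and footnote 17** cover one related case. A patient given systemic corticosteroids (or an increased dose) for an exacerbation in the last 4 weeks of treatment skips the week-12 constant work rate test (CWRET) but is followed for the other assessments.

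**The concern.** A randomized patient who develops, say, an injury or a cardiac finding meets two instructions. Section 3.3 ends participation; 8.5.2 ends dosing and tries to keep the patient. A site could follow either one and cite the protocol for it.

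At stake is follow-up of a treated patient after what may be a safety event, and week-12 data that need no exercise test. The protocol wants such data. Table 3 says "Treatment discontinuation: Data collected after the intercurrent event will be included in the analyses (Treatment policy strategy", and 11.4.3.2 carries the same or a similar method to the secondary endpoints. Three of the four listed secondary endpoints come from accelerometry, and the pre-exercise part of the fourth (FEV1) can be measured at rest. SAP 6.1 plans no imputation, so a value that is not collected stays missing.

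**Working it through.** **1. The plan's own figure.** The plan gives no number on this point. The nearest is the power statement in Protocol 11.2 (more than 85%). Completers per arm: 70 × 0.90 = 63. Standard error: 190 × √(2/63) = 33.85 s. Power: Φ(105/33.85 − 1.96) = Φ(1.14) ≈ 87%. The figure reproduces and the conflict does not alter it, because a patient still unfit at week 12 has no CWRET under either rule.

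**2. Where the rules overlap.** Protocol 8.1 gives the regimen after the loading dose as "300 mg Q2W from week 2 to week 10 or matching placebo". From day 1 until the last dose at week 10 (day 71) there is drug left to stop, so both rules apply.

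| Question | 3.3 | 8.5.2.1 with 8.5.2 |
|---|---|---|
| Trigger | Investigator judges patient unsuitable for exercise | Condition that rules out exercise develops |
| Study drug | Ends with participation | Permanently stopped |
| Participation | Cannot continue | Encouraged to continue |
| Remaining visits | One early termination visit (9.1.2) | All |

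**3. Is there a tie-breaker?** Section 7.3 does not supply one. Its caution against unnecessary withdrawal favours keeping the patient, but its clause on patients who cannot follow procedures could justify removal. Footnote 4 leans towards 3.3. Section 9.2.3.3 says the ECG is there to rule out a contraindication to the test, which suggests a condition for the test only. The SAP does not address the question.

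**4. Contacts and days lost under 3.3.** From Table 1, visits 6, 7 and 8 are by phone and visits 9 and 10 are in clinic. The days are 29 (week 4), 43 (week 6), 57 (week 8), 85 (visit 9) and 99 (visit 10). A withdrawn patient is asked to "return to the clinic once for an early termination visit consisting of the end of study assessments", so one visit is added back.

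| Removed at | Visits lost | Net of early termination visit | Days of follow-up lost, at most |
|---|---|---|---|
| Week 4 | 6 to 10: 5 (3 phone, 2 clinic) | 5 − 1 = 4 | 99 − 29 = 70 |
| Week 6 | 7 to 10: 4 (2 phone, 2 clinic) | 4 − 1 = 3 | 99 − 43 = 56 |
| Week 8 | 8 to 10: 3 (1 phone, 2 clinic) | 3 − 1 = 2 | 99 − 57 = 42 |

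The days are upper bounds. They assume that the early termination visit falls on the day of removal, which the protocol does not state.

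**5. What those days carry.** Section 10.1.1 says "AEs should be followed until they are resolved or last study visit, whichever comes first", so an earlier last visit shortens follow-up of unresolved non-serious events. Week-12 accelerometry, questionnaires and resting spirometry are lost too. This assumes that they belong to visit 9 and not to the end-of-study assessments: the columns of Table 1 are broken in the text, but the last mark in those rows sits with the week-12 CWRET. Section 10.1.1 follows serious events and events of special interest until they resolve or are clinically stable, so those are not cut short.

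**6. Visit 9.** Dosing is over, so 8.5.2 is not engaged. Footnote 4 read literally would cost visit 10: 99 − 85 = 14 days at most.

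**The case against.** The strongest answer is that 3.3 concerns entry only. The sentence sits in a narrative on risk, after text on screening evaluation, and its operative counterpart is exclusion criterion 38. Patients may take up to three incremental tests and three run-in CWRETs before randomization, so continuing has a natural meaning in that period. This reading is possible. It is not stated: the sentence covers any patient, sets continuing beside enrolling, and footnote 4 uses the same idea before every test, week 12 included.

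A second answer reads the sections together: 8.5.2 governs drug, and 7.3 leaves withdrawal to the investigator's judgement. The 8.5.2.1 list itself includes withdrawal of consent, so it is not purely a list of patients who stay. This has force and narrows the conflict. It does not remove it, because 3.3 is worded as a prohibition and 8.5.2 as encouragement to remain without exception.

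A sponsor may also prefer to let unfit patients leave an exercise study. That is a legitimate choice, but the protocol should then say so in 8.5.2.

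A reader might take footnote 4 as a second, separate conflict at visit 9. The documents do not support giving it that weight. Section 6.1 gives all patients a visit 2 weeks after treatment, and 9.2.3.3 gives the ECG a purpose limited to the test. It is a wording issue that supports the main point.

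**Conclusion.** The inconsistency is real and minor, with moderate confidence because the narrower reading of 3.3 cannot be excluded. Its size is per patient: a net 2 to 4 contacts and at most 42 to 70 days for removal between weeks 8 and 4, plus the week-12 non-exercise data. The documents give no frequency, and few patients are likely. SAP 2.1 expects the study to close with about 40 patients, which also limits the reach of any change.

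A reader might infer bias in the primary result. The documents do not support that. A patient still unfit at week 12 lacks the CWRET whichever rule is followed. The protocol's imputation rules could have sent that missing value to baseline carried forward or to multiple imputation, depending on how the patient left. SAP 5.7.1 and 6.1 make this moot: the summary is descriptive and nothing is imputed. Nor is this a gap in exercise safety, since both rules keep an unfit patient off the ergometer.

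**What to change.** 1. In 3.3, say that a patient judged unsuitable cannot enroll or, once randomized, cannot undergo further exercise testing.
2. In footnote 4, make a clean ECG a condition for performing that exercise test, and a condition of eligibility only before randomization.
3. In 8.5.2, add that a randomized patient who cannot exercise stops any remaining study drug, omits the CWRET and is asked to complete all other assessments through visit 10. Resting spirometry at visit 9 would be done when the investigator judges it safe.

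The late-exacerbator rule in 8.4 is the model, but it cannot simply be copied for spirometry. Section 9.2.2.5 first says that those patients will have it at rest, then, like footnote 20, leaves it to the investigator's discretion. Item 3 follows the discretionary wording.

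The cost is amended wording in two places and one added sentence. No visit, test or staff is needed beyond Table 1, and patients may still decline the remaining visits.
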